4.1 Primary endpoint

4.1.1 Objectives:

The primary objective of this study will be to evaluate the safety and feasibility of time varying caloric vestibular stimulation (tvCVS), delivered with a solid-state TNM™ Device, in people with mild/moderate Parkinson's disease dementia (PDD).

4.1.2 Endpoint:

The primary endpoints of this study are the following:

- Safety will be evaluated by evaluating whether tvCVS is associated with a worsening of PD signs and symptoms according to The International Parkinson and Movement Disorder Society Unified Parkinson's Disease Rating Scale Total Score: composite score of Parts I, II and III.

Adverse events will also be monitored.

- Feasibility:
 - Retention rate or the percent of participants that complete assessments required for analysis of the secondary endpoint:
 - High retention: >90%
 - Moderate retention: 60-90 %
 - Low retention:< 60 %
 - Treatment adherence rate during the 12-week treatment period:
 - High adherence: >84%
 - Moderate adherence: 55-84 %
 - Low adherence: < 55 %

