10.1 Sample Size Determination

This single-arm exploratory clinical trial will continue with competitive enrollment until 12 participants receive at least 1 treatment with the study Device. An enrollment number of 12 was set ensure adequate evaluation of the safety and the feasibility of the study design. Based on the Go/No Go Decision criteria for a follow-on Phase II RCT in PDD, this Phase I study would need to demonstrate that there were no Serious Adverse Device Effects (SADEs) and that at least 75% of the participants completed the end of treatment visit. This second criterion would mean that at least 9 participants complete the MoCA at the end-of-treatment visit without any SADEs. Utilizing a Poisson distribution, fulfilling these two criteria would yield 95% probability that the true probability of a serious adverse event among the PDD population would be less than 0.33. If all 12 participants completed the MoCA at the end-of-treatment visit without any SADEs, then the study would yield 95% probability that the true probability of a SADEs among the PDD population would be less than 0.25. This relationship is depicted in the following figure:

The likelihood of the population mean being at least that of the outcome's MCID can be determined as a function of the average change in MDS-UPDRS Total score among the sample. The figure below depicts the relationship between the sample (n=12) mean change in MDS-UPDRS Total Score and the likelihood that the true population mean change is 6.70 points (MCID). To illustrate the usefulness of the below figure, if the average change in MDS-UPDRS Total Score among the sample is 12.9 points, then there would be a 90% likelihood that the true population mean change is 6.70 points (i.e., the MCID value) indicating a clinically meaningful worsening of Parkinson's disease signs and symptoms

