2. STUDY DESIGN

This is a single arm study designed to evaluate the safety and feasibility of twice daily time-varying caloric vestibular stimulation (tvCVS) treatments using a solid-state Device developed by Scion NeuroStim, Inc. (SNS), also known as ThermoNeuroModulation (TNMTM), in patients with mild/moderate Parkinson's disease dementia (PDD) and to collect initial evidence to support proof of concept for the treatment of mild/moderate dementia in Parkinson's disease (PD). Participants will self-administer (with assistance, if necessary) ~19-minute *BID* treatments of tvCVS treatment over a period of 12 weeks (84 days). The study will be conducted at 2 centers located in the United States. This single-arm exploratory clinical trial will continue with competitive enrollment until 12 participants receive at least 1 treatment with the study Device at which point competitive enrollment will be closed.

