2.2. STUDY ENDPOINTS

Primary Endpoints

• Safety will be evaluated by determining whether tvCVS is associated with a worsening of PD signs and symptoms according to The International Parkinson and Movement Disorder Society Unified Parkinson's Disease Rating Scale (MDS-UPDRS) combined measure of Parts I, II, and III (Goetz, Tilley et al. 2008). This endpoint will evaluate the change in the summed score of MDS-UPDRS Parts I, II and III at the end of the treatment period (day 84), which is defined based on the change relative to baseline (day 0) score.

Adverse events will also be monitored.

- Feasibility will be defined by evaluating both retention rate and treatment adherence rate. Specifically,
 - Retention rate will be defined by the percentage of participants that complete assessments required for analysis of the secondary endpoint:
 - High retention: >90%
 - Moderate retention: 60-90%
 - Low retention: < 60%
 - Treatment adherence rate for each participant will be defined as the percentage of twice-daily treatments with the neuromodulation device completed during the 12-week treatment period:
 - High adherence: >84%
 - Moderate adherence: 55-84%
 - Low adherence: < 55%

Secondary endpoint: The secondary endpoint will evaluate change in the Montreal Cognitive Assessment (MoCA).

Exploratory endpoints: The following outcome measures will be used:

- The Zarit Burden Interview of Caregivers (ZBI)
- The Patient Global Impression of Improvement (PGI-I)
- The Neuropsychiatric Inventory Questionnaire (NPI-Q)
- The Modified Schwab and England Activities of Daily Living Scale (S & E)
- A customized cognitive battery (CCB) which will assess the following functions:
 - Memory
 - Hopkins Verbal Learning Test-Revised (total learning)
 - Hopkins Verbal Learning Test-Revised (delayed recall)
 - Hopkins Verbal Learning Test-Revised (recognition discrimination)
 - o Visuospatial
 - Neuropsychological Assessment Battery Visual Discrimination
 - o Language
 - Delis-Kaplan Executive Function System Semantic Fluency
 - Attention
 - Neuropsychological Assessment Battery Digits Forward
 - Hopkins Verbal Learning Test-Revised (Trial 1)
 - Processing speed
 - Oral Symbol Digit Modality
 - Executive Function
 - Delis-Kaplan Executive Function System Semantic Fluency Switching
 - Neuropsychological Assessment Battery Digits Backward

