4. SAMPLE SIZE DETERMINATION

An enrollment number of 12 was set ensure adequate evaluation of the safety and the feasibility of the study design. Based on the Go/No Go Decision criteria for a follow-on Phase II randomized controlled trial (RCT) in PDD, this Phase I study would need to demonstrate that there were no Serious Adverse Device Effects (SADEs) and that at least 75% of the participants complete assessments required for analysis of the secondary endpoint. This second criterion would mean that at least 9 participants complete the MoCA at the end-of-treatment visit without any SADEs. Utilizing a Poisson distribution, fulfilling these two criteria would yield 95% probability that the true probability of a serious adverse event among the PDD population would be less than 0.33. If all 12 participants completed the MoCA at the end-of-treatment visit without any SADEs, then the study would yield 95% probability that the true probability of a SADEs among the PDD population would be less than 0.25. This relationship is depicted in the following figure:

The likelihood of the population mean being at least that of the outcome's MCID can be determined as a function of the average change in MDS-UPDRS Total score among the sample. The figure below depicts the relationship between the sample (n=12) mean change in MDS-UPDRS Total Score and the likelihood that the true population mean change is 5.20 points (MCID).

To illustrate the usefulness of the above figure, if the average change in MDS-UPDRS Total Score (i.e., the combined measure of Parts I, II and III) among the sample is 6.2 points, then there would be a 80% likelihood that the true population mean change is 5.20 points (i.e., the MCID value) indicating a clinically meaningful worsening of Parkinson's disease signs and symptoms.

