6.1. ANALYSIS POPULATIONS

Intent-to-treat Population (ITT): All participants who start at least one treatment with the study device will be included in this primary analysis of efficacy and safety.

Per-protocol Population (PP): All eligible participants who (1) demonstrate at least 70% adherence of the randomized expected treatments with the Study Device and (2) have completed the regularly scheduled end of treatment visit (day 84), and (3) have not had changes to medications used to treat motor and/or non-motor symptoms of PD during the trial will be included in the PP population.

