6.6.1 PRIMARY ENDPOINTS

(Safety) MDS-UPDRS Parts I, II & III summed score: Changes will be considered to be clinically meaningful worsening if the median difference meets or exceeds the previously established MCID (+5.2 points for clinical worsening) (Makkos, Kovacs et al. 2018). Two-sided, 90% confidence intervals for the combined MDS-UPDRS Parts I, II, and III scores at baseline and the end of treatment period will be constructed. If the median difference (baseline- end of treatment) is less than 5.2 and the confidence interval of the difference (baseline – end of treatment) contains 5.2, then the no clinically meaningful worsening.

(Feasibility)

- **Retention rate** will be defined by the percentage of participants that complete assessments required for analysis of the secondary endpoint:
 - High retention: >90%
 - Moderate retention: 60-90 %
 - Low retention: < 60 %
- **Treatment adherence** rate for each participant will be defined as the percentage of twice-daily treatments with the neuromodulation device completed during the 12-week treatment period:
 - High adherence: >84%
 - Moderate adherence: 55-84 %
 - Low adherence: < 55 %
 - Treatment adherence is captured by the study device and will be reported summarized with minimum, 1Q, median, 3Q, and maximum values. Treatment adherence of \geq 70% is required for inclusion in the Per Protocol cohort.

Adverse Events (AEs): Participants will be assessed for AEs every two weeks at minimum (either at study visits or during phone calls). For each group, the AEs will be summarized with frequency and percentage by preferred (PT) term, with all participants in that treatment group as the denominator. Classification will utilize MedDRA System Organ

Class (SOC) based on MedDRA® Version 26.0 or other terminology/classification common to Parkinson's disease (e.g., falls, freezing of gait, etc.). AE incidence will be summarized by both severity and causal relationship to Device treatment (as determined by the blinded Principal Investigator or designated study personnel). AEs deemed to be of "possible" or "probable" relationship or "related" to the Device will also be considered as device related. Additionally, the number of events and number of device-related events per person will be reported as a distribution.

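### The MDS-UPDRS safety verdict is a group-level rule with a reversed interval condition and no count of individual worsening, so it can return a reassuring result when a quarter to a half of 12 participants have worsened

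*SAP*

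**What the plan says.** Protocol 4.1.2 frames the question broadly: "Safety will be evaluated by evaluating whether tvCVS is associated with a worsening of PD signs and symptoms". SAP 2.2 narrows it to one number per participant: "This endpoint will evaluate the change in the summed score of MDS-UPDRS Parts I, II and III at the end of the treatment period", taken relative to baseline.

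SAP 6.6.1 then gives two sentences of decision rule. The first declares harm: "Changes will be considered to be clinically meaningful worsening if the median difference meets or exceeds the previously established MCID", with the threshold given as "5.2 points for clinical worsening". The second gives the reassuring conclusion when two conditions hold together: the median of baseline minus end of treatment is below 5.2, and the 90% confidence interval of that difference contains 5.2. The interval method is not named. SAP 6.5 makes the Wilcoxon signed-rank test the default for paired comparisons.

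The analysis set is broad: "All participants who start at least one treatment with the study device will be included in this primary analysis of efficacy and safety". Adverse events also sit under the primary endpoints and are tabulated per participant.

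Neither document plans a count or proportion of participants whose summed score rises by the MCID, or an analysis of change in Parts I, II and III separately. Items from Parts II and III are used on their own only to classify motor phenotype at baseline (SAP 6.4.2). Protocol 10.1 uses a different MCID, referring to "the likelihood that the true population mean change is 6.70 points (MCID").

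**The concern.** A group median of 12 changes depends on the sixth and seventh ordered values, so the size of the worst five changes does not affect it. An interval can make up for this, but only if it is used to rule out the MCID. Here the interval has to include the MCID, so a wide interval produced by badly affected participants helps the reassuring verdict along. Summing the three Parts adds a second route, because improvement on non-motor items can offset worsening on the motor examination.

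At stake is what the trial may claim. This is a first study of the device in a population that Protocol 9.6 calls vulnerable, and it precedes a randomised trial. A statement that the device did not worsen Parkinson's signs and symptoms should not be available when a sizeable minority, or half, of the users worsened by more than the MCID and no planned table shows it.

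**Working it through.** **Inputs.** n = 12 treated (SAP 2: "until 12 participants receive at least 1 treatment with the study Device at which point competitive enrollment will be closed"). At least 9 completers for the go decision (SAP 4: "at least 9 participants complete the MoCA at the end-of-treatment visit without any SADEs"). MCID 5.2 (SAP 6.6.1) or 6.70 (Protocol 10.1). Two-sided 90% interval. The individual changes below are constructed examples, not forecasts.

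**1. The plan's own figure.** The zero-event Poisson bound is −ln(0.05)/n: 2.996/9 = 0.333 and 2.996/12 = 0.250, matching the stated 0.33 and 0.25. This concerns serious adverse device effects and says nothing about the scale.

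**2. Intervals at n = 12** (worsening positive).
- Sample median: mean of the 6th and 7th ordered changes. For the distribution-free interval from the k-th to the (13−k)-th value, coverage is 1 − 2·ΣC(12,x)/2¹², x = 0 to k−1. The 4th to 9th values give 85.4% and the 3rd to 10th give 96.1%, so the latter is the narrowest with at least 90%.
- Hodges-Lehmann: median of the 12·13/2 = 78 pairwise averages. The exact signed-rank interval runs from the 18th to the 61st average (coverage 90.8%).

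**3. The rule as written, sign taken as intended.**

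| Changes | Sample median (interval) | Verdict | Hodges-Lehmann (interval) | Verdict |
|---|---|---|---|---|
| 5 at +30, 7 at 0 | 0 (0 to 30) | no worsening | 15 (0 to 15) | worsening |
| 3 at +30, 9 at 0 | 0 (0 to 30) | no worsening | 0 (0 to 15) | no worsening |
| 6 at +10, 6 at 0 | 5.0 (0 to 10) | no worsening | 5.0 (0 to 10) | no worsening |

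Example of the count behind row 2: nine zeros give 9·10/2 = 45 averages of 0, 9·3 = 27 of 15 and 6 of 30. The 39th and 40th are 0 and the 61st is 15. Every verdict in the table is the same with 6.70 in place of 5.2.

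In row 1, 5/12 = 42% (exact 95% interval 15% to 72%) worsened by 30/5.2 = 5.8 times the MCID. With 9 completers, four at +20 and five at 0 still give a sample median of 0.

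**4. Literal sign.** As baseline minus end of treatment, row 1 becomes median 0 with interval −30 to 0. That excludes +5.2 and the median does not reach 5.2, so neither sentence applies and there is no verdict.

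**5. The interval condition also fails in the other direction.** Changes of −6, −5, −4, −3, −2, −1, 0, 1, 2, 2, 3, 3 give a median of −0.5 and interval −4 to 2. No one worsened by 5.2, yet the interval excludes 5.2 and the rule withholds the reassuring verdict.

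**6. If the condition is corrected** to upper 90% limit below the MCID, all three rows are blocked under either estimator (upper limits 30, 30, 10 and 15, 15, 10). What can still pass is smaller. Two at +30 and ten at 0 give a distribution-free interval of 0 to 0, because the 10th value is 0. One at +30 and eleven at 0 give 11·12/2 = 66 zero averages, so the 61st is 0 and the signed-rank interval is 0 to 0 as well.

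**7. Background noise.** No SD of change is stated. The SAP illustration (6.2 against 5.2, 80%) implies 1.0·√12/0.842 = 4.1. The protocol illustration (12.9 against 6.70, 90%) implies 6.2·√12/1.282 = 16.8. Assuming normal changes with true mean 0, the chance that one participant exceeds 5.2 is 10% (SD 4.1) to 38% (SD 16.8), or 1.2 to 4.5 of 12.

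**The case against.** The strongest reply is that safety does not rest on this median. The rule has an interval condition. Adverse events are part of the primary endpoint, are assessed at least every two weeks, and are tabulated by severity, device relationship and participant, with Parkinson's-specific terms. Zero serious adverse device effects is a go criterion, two or more serious related events pause enrolment, and an independent medical monitor reviews safety. A reader might infer from the table that the whole safety conclusion depends on a group median, or that a median-based rule can never register harm in a minority. The documents do not support either inference. The adverse event provisions stand, and step 6 shows that a median with a correctly directed interval does respond to three of 12.

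A second reply is that the five-of-12 case depends on the reading. It needs the sample median, whereas the Hodges-Lehmann estimate that goes with the signed-rank test flags it, and it needs the opposite sign to the one printed. That also stands. It narrows the example but does not remove the problem, because rows 2 and 3 pass under either estimator.

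Third, a participant count is noisy without controls, and offsetting between Parts is a property of any composite. Both are true, and they limit the count and the Part-level table to description.

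One gap remains. Nothing in either document makes a rise in the score an adverse event, and the go and pause rules respond only to serious device-related events. A non-serious individual worsening on the chosen safety scale need not appear in any planned table.

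**Conclusion.** The point holds for the MDS-UPDRS component of primary safety. As written, with worsening taken as positive, the rule can return the reassuring verdict with three of 12 participants at +30 or six of 12 at +10 under either estimator, and with five of 12 at +30 if the sample median is used. Under the printed sign the five-at-+30 case gives no verdict.

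The main cause is the interval condition, which asks for inclusion of the MCID where it should ask for exclusion. The missing participant-level count is a separate and smaller gap, which remains after that condition is corrected (one or two severe worseners can still pass). It would be too strong to say that five of 12 can always worsen unnoticed, or that the follow-on trial decision turns on this verdict: the go criteria in SAP 4 are serious adverse device effects and retention.

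The conclusion rests on constructed samples with complete Day 84 data and on the intended sign being end of treatment minus baseline, which is how SAP 2.2 describes the change. It does not depend on which of the two MCIDs is used.

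**What to change.** In SAP 6.6.1:

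1. Define the change as end of treatment minus baseline. Name the estimator and the interval method. Conclude no clinically meaningful worsening only if the upper 90% limit lies below the MCID.
2. Report the number and percentage of treated participants with Day 84 data whose summed score rises by at least the MCID, with an exact 95% interval and a listing. State any no-worsening conclusion next to that count. For scale, 0 of 12 would give an exact upper limit of 1 − 0.025^(1/12) = 26%.
3. Tabulate the change in Parts I, II and III separately.
4. Reconcile the MCID between SAP 6.6.1 (5.2) and Protocol 10.1 (6.70), so that the rule and the count use one pre-stated value.

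The cost is a rewritten rule, a few added sentences and two small tables. No new data are needed, since all three Parts are already scheduled at baseline, Day 42 and Day 84. The price is some awkwardness in reading the results: with no control arm, ordinary fluctuation will put some participants over the threshold (step 7). The SAP should therefore say that the count is descriptive and does not replace the group rule.

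### The MDS-UPDRS safety rule clears the device only when the 90% CI still contains the worsening MCID, and it prints the difference with the wrong sign

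*SAP*

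**What the plan says.** SAP 6.6.1 holds the only decision rule for the MDS-UPDRS Parts I–III component of the primary safety endpoint. Protocol 10.2 refers statistical detail to the SAP. The rule has three parts.

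- Worsening is declared if the median difference "meets or exceeds the previously established MCID (+5.2 points for clinical worsening"). No subtraction order is given here.
- The intervals to be built are "Two-sided, 90% confidence intervals for the combined MDS-UPDRS Parts I, II, and III scores at baseline and the end of treatment period".
- The favourable verdict has two conditions. The one on the point estimate is worded "If the median difference (baseline- end of treatment) is less than 5.2". The one on the interval, which must hold as well and which carries the verdict, is worded "the confidence interval of the difference (baseline – end of treatment) contains 5.2, then the no clinically meaningful worsening".

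Elsewhere, SAP 2.2 describes the endpoint as the day 84 change, "which is defined based on the change relative to baseline (day 0) score". The example in SAP 4 takes a positive sample mean change of 6.2 and speaks of a likelihood that "the true population mean change is 5.20 points (i.e., the MCID value) indicating a clinically meaningful worsening". The parallel example in Protocol 10.1 uses a different threshold for the same score: "the true population mean change is 6.70 points (i.e., the MCID value) indicating a clinically meaningful worsening".

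**The concern.** There are two main faults and two lesser ones.

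1. **Interval condition.** The rule requires the interval to include the harm threshold. That outcome means worsening by the MCID has not been ruled out. The outcome that does rule it out, an interval wholly below 5.2, leads to no stated conclusion. A wider interval is more likely to contain 5.2, so imprecision helps the device pass. This holds under either sign.
2. **Sign.** Higher scores are worse, so baseline minus end of treatment makes worsening negative. That conflicts with the +5.2 in the same paragraph and with the example in SAP 4. With the printed sign, +5.2 is an improvement, and a worsening of 5.2 (a value of −5.2) is never examined.
3. **Which interval.** The text constructs intervals for the scores at the two visits, but the decision uses an interval for the paired difference, for which no method is named.
4. **Threshold.** The SAP uses 5.20 and the Protocol 6.70.

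At stake is the answer to whether Parkinson's signs and symptoms worsened on treatment. The adverse-event summaries and the Go/No-Go criteria (no SADEs, at least 75% completion) are separate and are not affected.

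**Working it through.** **The plan's own figures.** Neither document states an SD for the change, so the worked examples cannot be reproduced, only solved backwards. Reading the likelihood as Φ((mean − MCID)/(SD/√12)):

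- SAP 4: (6.2 − 5.2)/(SD/√12) = 0.8416 for 80%, so SD = 1.0 × 3.464/0.8416 = 4.1.
- Protocol 10.1: (12.9 − 6.70)/(SD/√12) = 1.2816 for 90%, so SD = 6.2 × 3.464/1.2816 = 16.8.

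The range 4.1 to 16.8 is therefore an assumption. The two examples imply SDs about four-fold apart.

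**Inputs.** n = 12 (SAP 4), with 9 completers as the Go/No-Go minimum; MCID 5.2, with 6.70 as a check; two-sided 90% interval. The interval is taken as the exact signed-rank interval, to match the test in SAP 6.5. Its one-sided error is 4.6% at n = 12 and 4.9% at n = 9. Changes are drawn from a normal distribution, 40,000 simulated trials per setting.

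**Step 1: three data patterns against the written rule.** Patterns (a) and (b) use end of treatment minus baseline.

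- (a) Median −3.0, interval −5.0 to −1.0. MCID worsening is excluded, but the rule gives no verdict.
- (b) Median 4.5, interval −1.5 to 11.0. Worsening of twice the MCID is still compatible, but the rule concludes no meaningful worsening.
- (c) All twelve participants worsen, by a median of 14.5. With the printed sign this is −14.5, interval −16.0 to −12.5, and it is not flagged.

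**Step 2: sign corrected, containment kept, true worsening equal to the MCID.** The sample median falls below the threshold in half of trials. In about 4.6% the upper limit also falls below it, and those trials lose the verdict. The rest are cleared: 50% − 4.6% ≈ 45%. With 9 completers it is 50% − 4.9% ≈ 45%. The simulation gives about 45% at every SD and with either MCID. A rule requiring the upper limit to be below the MCID clears 4.4–4.8% at n = 12 and about 5% at n = 9.

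**Step 3: no true change, n = 12, MCID 5.2.** The written rule gives the same result under either sign.

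| SD of change | Written rule clears | Upper limit below MCID clears |
|---|---|---|
| 4.1 | 1% | 99% |
| 8 | 32% | 65% |
| 12 | 52% | 38% |
| 16.8 | 58% | 24% |

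The written rule passes more often as the data get noisier; the upper-limit rule does the reverse.

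**Step 4: effect of the sign, n = 12, SD 4.1 to 16.8.**

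- Printed sign throughout: a true 10-point worsening is flagged in 0–0.4% of trials, cleared in 0–12%, and gets no verdict in 88–100%. A true 10-point improvement is flagged as worsening in 80–100%.
- Worsening sentence read as end of treatment minus baseline, final sentence as printed: a true 10-point worsening is flagged in 80–100%. At SD 16.8, however, both opposite conclusions apply to the same trial in 5.4% (no change) to 6.0% (MCID worsening). At SD 12 and below this happens in about 1% or less.

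**The case against.** The best defence is that this is a clerical slip. The sentence is visibly garbled, and with the sign aligned and the word not inserted before the verb, the rule becomes in practice the upper-limit rule. That may be what was meant. But the inserted word is not enough. With the printed sign, worsening pushes the interval below +5.2, so that patch alone would clear a true 10-point worsening in 88–100% of trials. Both the condition and the sign need correction, and choosing the reading after the data are seen would be a post hoc choice on a primary safety endpoint.

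Other points have some force:

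- A reader could infer from the first sentence that a median below 5.2 is not worsening. The SAP never states that verdict, and the inference would ignore the interval altogether.
- Applying the printed sign to every sentence is the least likely reading, so the 80–100% false-flag figures show an ambiguity rather than predict an analysis.
- SAP 2.2 gives no explicit subtraction order. The sign conflict rests on SAP 6.6.1 itself and the example in SAP 4.
- SAP 6.5 names the signed-rank test for paired data, which points to a matching interval, though it names a test and not an interval.
- The MCID mismatch is a separate discrepancy and causes neither logical fault.
- The 45% follows almost directly from setting the true change at the threshold. That is why it does not depend on the SD.
- The study is small and exploratory, and Go/No-Go does not use this rule. That limits the consequences but does not make the pre-specified rule valid.

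**Conclusion.** The concern holds and should be corrected before analysis. The logical fault is visible in the text and needs no assumed SD: the only stated route to a favourable conclusion requires that MCID-sized worsening has not been excluded, and the printed sign contradicts the threshold in the same paragraph. With the sign corrected and the containment condition kept, a true worsening equal to the MCID is cleared in about 45% of trials, roughly ten times the rate under an upper-limit rule. That contrast does not depend on the SD, on which MCID is used, or on having 12 or 9 completers. The figures for no true change (1% to 58%) and for a 10-point change rest on the assumed SD range of 4.1 to 16.8, normally distributed changes and a signed-rank interval. Correcting the sign alone, or inserting the missing negative alone, does not repair the rule.

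**What to change.** In SAP 6.6.1:

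1. Define change as end of treatment minus baseline in every sentence, so that positive means worse.
2. Replace the per-visit intervals with one two-sided 90% interval for the paired median change (Hodges–Lehmann, consistent with the signed-rank test), and use the same estimate for the point rule. The estimate always lies inside its interval, so the verdicts cannot overlap.
3. Conclude no clinically meaningful worsening only if the upper limit is below the MCID; conclude clinically meaningful worsening if the estimate is at or above it; otherwise report the result as inconclusive.
4. Reconcile the MCID between the SAP (5.20) and Protocol 10.1 (6.70) before analysis, and give the source of the value kept.

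The cost is a few sentences in the SAP and one line to align the two documents; no data, visits or participants are added. The downside is that the favourable verdict is harder to earn when variability is large. With no true change and n = 12, it is reached in about 99%, 65%, 38% and 24% of trials at SD 4.1, 8, 12 and 16.8 with MCID 5.2, or in about 100%, 83% and 34% at SD 4.1, 8 and 16.8 with MCID 6.70. In the remaining trials most results would be labelled inconclusive, which is what 12 participants can support at that variability.
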